### **9.3 Institutional Review Board**

It is the responsibility of the Investigator to submit the protocol, consent form and information sheet to the IRB. An IB will be available for review by the IRB. The protocol and informed consent form (ICF) must be approved by the IRB prior to the recruitment of the first subject. The template consent form may be revised in accordance with site-specific requirements with Sponsor review and approval. A copy of the IRB written approval must be provided to the Sponsor and investigator before the trial may start at that institution. Written approval from the IRB is also required for substantial protocol amendments prior to their implementation.

A substantial amendment may arise from changes to the protocol or from new information relating to the scientific documents in support of the trial. Amendments are “substantial” when they are likely to have an impact on:

- the safety or physical or mental integrity of the subjects;
- the scientific value of the trial;
- the conduct or management of the trial; or
- the quality or safety of any IP used in the trial.

If it is necessary to change or deviate from the protocol to eliminate an immediate hazard to the subjects, the Investigator will notify the Sponsor and the IRB of the new events and the measures taken as soon as possible.

The Investigator will report promptly to the Sponsor and IRB any new information that may adversely affect the safety of the subjects or the conduct of the trial. On completion of the trial, the Investigator will inform the applicable IRB as per local IRB requirements that the trial has ended. If the study is terminated for any reason, the investigator will return all clinical supplies and study-related equipment supplied by the Sponsor to the Sponsor unless otherwise specified.

### **9.4 Schedule of Events**

NEWS2 Assessments, laboratory assessments, SARS-CoV-2 testing, and other observations will be conducted by experienced personnel throughout the study based on the Schedule of Events. The majority of study information is to be collected from the EHR. Phone calls or other digital media and outpatient visits for hematology/chemistry samples may be required to complete some study assessments if the subject is discharged prior to Study Day 15.

PROTOCOL NUMBER: CCB-CRISIS-01  
PROTOCOL VERSION DATE: 01MAY2020

Page 32 of 55

See [15.1 Schedule of Events in Appendix A](#) for the full list of study assessments and timings.

Blood chemistry tests include blood urea nitrogen (BUN), creatinine, alkaline phosphatase (ALP), alanine amino transferase (ALT), aspartate amino transferase (AST), bilirubin, total protein, albumin, glucose, serum electrolytes (sodium, potassium, chloride, carbon dioxide/bicarbonate, and calcium), lactate dehydrogenase (LDH).

Inflammatory markers including D-dimer, ferritin, CRP, ESR, troponin, fibrinogen, and procalcitonin may be collected locally if available by the Institution. Additional inflammatory markers will be collected and analyzed by a central laboratory, as specified in the Laboratory Manual. A sample is to be collected for DHO and brequinar pharmacokinetics at the timepoints specified in the Laboratory Manual.

Hematology tests include hemoglobin, hematocrit, complete blood count with full differential, and platelet count.

Nasopharyngeal swabs for SARS-CoV-2 viral load, inflammatory markers, and DHO samples will be collected Days 1, 3, 5, 7, and 15 (collection instructions available in the supplied Laboratory Manual).

NEWS2 Criteria are available in [Appendix C Section 15.3](#).

Hospitalization status is to be recorded as hospitalized not in ICU, hospitalized in ICU, or discharged.

## 9.5 Study Conduct

### Screening Visit (Since hospital admission)

These procedures must be completed since hospital admission and prior to starting dosing. Obtain the subject's written informed consent (be sure to note time of consent), then collect baseline information from the EHR. Do not perform study specific procedures for data available from the EHR. For Screening/Day 1 use the EHR results closest to the visit to confirm subject eligibility.

- Demographics (date of birth, gender, race, ethnicity, height and weight).
- Recent (within one year unless ongoing), relevant medical/surgical history and concomitant medications.
- Date of first symptom.
- Record any new or changed adverse events and new or changed concomitant medications since signing the ICF.
- Record any clinically significant abnormal physical examination findings as recorded in EHR.
- Hematology/chemistry from EHR.
- Ensure negative pregnancy test result is present in the EHR for women of childbearing potential (WOCBP).

PROTOCOL NUMBER: CCB-CRISIS-01  
PROTOCOL VERSION DATE: 01MAY2020

Page 33 of 55

- Polymerase chain reaction (RT-PCR) or other FDA-cleared commercial or public health assay for SARS-CoV-2 infection (may utilize test results from external laboratory to meet entry criteria provided such results are accurately documented and can be confirmed).
- Confirm subject meets all inclusion and no exclusion criteria.

## Treatment

The treatment period is up to 5 days: standard of care alone (SOC) or SOC + brequinar 100 mg daily for 5 days. Data points such as NEWS2 Assessments are to be collected from the EHR when possible, a separate visit by study staff is not to be conducted. The first dose of brequinar is to be given as soon as possible depending on availability of investigational pharmacy staff. If the subject is discharged from the hospital prior to Day 15, see Section 8.4 for how and when to conduct study assessments.

It is understood that some assessments may not be conducted if the subject is unable to return to the clinic after discharge due to restricted travel or if the study visit cannot be conducted remotely; this will not be counted as a protocol deviation. Collect information from the EHR, medication records and Progress Notes whenever possible

### Days 1 - 7 (8 AM ± 8 hours)

- If Day 1 is different date from Screening, confirm subject continues to meet all inclusion and no exclusion criteria.
- Randomize the subject (record date and time of randomization).
- Review Progress Notes and medication records to collect any new or changes to ongoing adverse events or new or changed concomitant medications since previous visit (may be omitted on Day 1 if Screening visit was conducted on same day as Study Day 1). Repeat on Day 7.
- Collect SOC hematology/chemistry results from the EHR on Day 1 (pre-dose) and Day 7 (may be omitted for Day 1 if Screening visit conducted on same date as Study Day 1). Ensure that Day 1 samples are obtained prior to first dose of study drug, if applicable.
- Days 1 (pre-dose), 3, 5, 7:
  - Collect NEWS2 Assessments from the EHR.
  - Collect results for inflammatory markers from EHR for those analyzed locally; collect, process and ship samples for DHO/brequinar PK and cytokine panel to be analyzed at the central laboratory per the Laboratory Manual.
  - Collect and process SARS-CoV-2 nasopharyngeal viral load samples.
  - Record hospitalization status (hospitalized, hospitalized in ICU, discharged) (Day 1 already recorded as part of Inclusion criteria, do not record again).
- Dispense study medication (Days 1 through 5 if in brequinar group) and record date and time of brequinar administration. Keep the drug administration interval as close as possible to 24h. Ensure Day 1 labs are drawn prior to first brequinar dose on Day 1. If a subject taking brequinar is discharged prior to Day 5, administer final dose on day of discharge. Do not give subject study drug to take home.

PROTOCOL NUMBER: CCB-CRISIS-01  
PROTOCOL VERSION DATE: 01MAY2020

Page 34 of 55

- Drug accountability Day 7  $\pm$  2 days.

**Final Visit Day 15** (8 AM  $\pm$  2 days) or Hospital Discharge Day if earlier than Day 15

- Review Progress Notes and the medication record to collect information for any adverse events or new concomitant medications since Day 7 (from EHR if subject still hospitalized, otherwise by phone or other digital media).
- Collect results for SOC hematology/chemistry from the EHR if subject still hospitalized.
- Collect inflammatory markers from EHR for those analyzed locally; collect samples for DHO and cytokine panel to be analyzed at the central laboratory if subject still hospitalized.
- Collect NEWS2 Assessments from the EHR.
- Collect nasopharyngeal viral load sample.
- Collect hospital status (hospitalized, hospitalized in ICU, discharged).

**Day 29** (8 AM  $\pm$  3 days)

- Determine survival status from EHR if available or contact the subject by phone call/digital media as acceptable to the institution.

If the subject is being discharged before Day 15, follow the procedures outlined in Section 8.4.

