--	--

	
they have assessments through Day 15, whether conducted in the hospital or contacted via phone or other digital media.

Safety/ Tolerability
	
Safety/Tolerability
 
Adverse events will be collected from the time of informed consent through Day 15. After Day 15, collect/record only Serious Adverse Events (SAEs) or those judged by the Investigator or designated person to be related to study drug, including but not limited to potential hematologic toxicities. Post-randomization adverse events will be those with an onset after the date and time of randomization.

Statistical Analysis
	
A separate, detailed statistical analysis plan (SAP) will be finalized prior to locking the database. All analyses of safety and efficacy for this study will be descriptive in nature and presented by group. Subject demographics and baseline characteristics will be summarized. Subject data listings will also be provided.
 
Summaries for quantitative variables will include the mean, median, quartiles, standard error, minimum, and maximum. For qualitative variables, the summaries will include the number and percentage of subjects for each outcome, and the 95% CI, when appropriate. Any statistical testing will be considered exploratory and descriptive. All computations will be performed using SAS® (Version 9.4 or higher). Safety and tolerability will be assessed in terms of AEs, SAEs, safety laboratory data, and NEWS2 Assessments.
 
Adverse event data will be descriptively evaluated. All AEs will be reported in data listings. The incidence of post randomization adverse events, defined as AEs occurring after randomization will be tabulated by Medical Dictionary for Regulatory Activities (MedDRA) preferred term and system organ class, and by severity and relationship to study treatment. All laboratory results, NEWS2 Criteria, and other clinical measures will be summarized using appropriate descriptive statistics.

PROTOCOL NUMBER: CCB-CRISIS-01  
PROTOCOL VERSION DATE: 01MAY2020

Page 15 of 55

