#### 8.2.1 Safety/Tolerability

Safety/tolerability is assessed for each subject at each study visit using the Common Terminology Criteria for Adverse Events v4.03 (CTCAE).

Adverse events (AEs) commonly observed in patients treated with brequinar are provided in the Investigator's Brochure (IB) and include thrombocytopenia, nausea, anemia, diarrhea, vomiting, leukopenia, stomatitis, rash, granulocytopenia, fatigue, and infection. In a study of 209 subjects treated once-weekly (DuP 785-012, see Brequinar IB [5]), the deaths of three patients were attributed to study drug toxicity (two to hemorrhage, one following acute renal failure). Severe toxicities grades (Grades 3 to 4) which typically led to discontinuation in this study included hematologic toxicities (anemia, thrombocytopenia, leukopenia, granulocytopenia), digestive system toxicity (nausea, vomiting, stomatitis, others including gastric hemorrhage) and mucositis.

In three oncology studies (Study 785-001 [16], 785-003 [17], and 785-005 [18]) with five consecutive days of intravenous (IV) brequinar dosing and 168 subjects, there were no toxic deaths. For subjects from these three studies who were treated with a dose of 100 mg or below (as will be dosed in CCB-CRISIS-01), AEs through 21 days showed that 2 of 39 subjects (5.1%) had a severe (Grades 3 or 4) AE related to study drug (1 subject each with hyperbilirubinemia and hyperglycemia), and no subjects discontinued from the study due to a study drug-related AE. The few study drug related AEs through 21 days at or below the 100 mg dose from these three studies included 2 subjects each with nausea, vomiting, and creatinine elevated and one subject each with thrombocytopenia and diarrhea. When only studies with oral dosing were considered at this dose level (Studies 785-022 [19], 785-031 [20], and 785-034 [21]), the study drug related AEs through 21 days (each observed in one subject only) included diarrhea, headache, nausea, pruritus, abdominal pain, anorexia, chest pain, dry mouth, fatigue, keratosis, stomatitis, and vomiting. See brequinar IB (5).

PROTOCOL NUMBER: CCB-CRISIS-01  
PROTOCOL VERSION DATE: 01MAY2020

Page 27 of 55

In most instances, brequinar-related toxicities were transient, clinically manageable and reversible upon discontinuation of brequinar treatment. Any of these events reported with brequinar use can be serious in nature and may result in death.

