## 10 ADVERSE EVENT REPORTING

An adverse event is any untoward medical occurrence in a patient or clinical trial subject administered a medicinal product and which does not necessarily have a causal relationship with this treatment. An AE can therefore be any unfavorable and unintended sign (including an abnormal laboratory finding), symptom, or disease temporally associated with the use of the medicinal product, **whether or not considered related to the medicinal product.**

Events that occur prior to informed consent will be entered as medical history; AEs that occur after informed consent will be entered on the AE form.

Subjects will be questioned and observed for evidence of AEs, whether or not judged by the Investigator or designated person to be related to study drug. All AEs will be documented in the subject's medical record and CRF. For any pre-existing condition or abnormal laboratory finding that changes in severity after dosing, this change should be recorded as an AE. New abnormal laboratory findings that are clinically significant are considered AEs.

All adverse events will be collected from the time of informed consent through Day 15. After Day 15, collect/record only Serious Adverse Events (SAEs) or those judged by the Investigator or designated person to be related to study drug. AE details are to be documented including start and stop date and times, whether continuous or intermittent, severity, any intervention utilized to correct the event (e.g., medication, surgery, or other therapy), outcome and the relationship to the study drug.

AEs identified in the protocol as critical to the evaluation of safety must be reported to the Sponsor by the Investigator according to the reporting requirements within the time periods specified in the protocol.

AEs determined by the Investigator to be related to study drug must be followed until resolution or until they are considered stable or for at least 30 days after discontinuation of study drug.

Any serious adverse events (SAEs) experienced after 30 days post the last dose of study drug should only be reported to the sponsor if the investigator suspects a causal relationship to the study drug.

Abnormal laboratory values or test results occurring after study enrollment constitute AEs only if they induce clinical signs or symptoms, are considered clinically significant, or require therapy.

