### **10.6 Safety Monitoring for Hematologic Toxicities**

Myelosuppression is a known effect of DHODH inhibition that is associated with prolonged exposure and high doses. To reduce the risk of this effect with brequinar in COVID-19 subjects, the extensive brequinar safety database with over 1,000 patients has been evaluated to select a dose

PROTOCOL NUMBER: CCB-CRISIS-01  
PROTOCOL VERSION DATE: 01MAY2020

Page 41 of 55

level expected to be safe and well tolerated with regard to hematologic toxicity. In addition to enhancing safety by selecting a relatively brief 5-day exposure and a low brequinar dose, all subjects in the clinical trial will initially be hospitalized as in-patients and will be under the care of highly qualified infectious disease, critical care, and associated medical personnel. As is standard of care for moderately to severely ill in-patients, daily samples will be obtained for hematology assessments including complete blood count with full differential (WBC, RBC, hemoglobin, hematocrit, platelet count, absolute neutrophils, absolute lymphocytes, absolute monocytes, absolute eosinophils, and absolute basophils). Any clinically significant out-of-range laboratory values will be assessed by hospital staff in a timely manner and treatment needs addressed as appropriate. Clinically significant out-of-range laboratory results will be reported as adverse events.

In addition to real time assessments by the treating clinical team, the Clear Creek Medical Monitor will assess the available hematology data on a weekly basis to identify any pathologic trends or safety issues. Any apparent increase in the expected rate or severity of hematologic safety events will be discussed with the Principal Investigators, the Sponsor, and the Medical Monitor. In addition, the Data Safety Monitoring Board will assess available hematology data on a periodic basis to independently assess any pathologic trends or safety issues. If the rate or severity of hematologic toxicities appears to be above the expected rate or the severity appears worse than that expected, the trial enrollment will be suspended and no further subjects will be treated while a comprehensive data review is conducted. Depending on the outcome of the safety review the study may be stopped, the design adjusted, or the study may continue as designed.

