## 15 APPENDICES

### 15.1 Appendix A: CCB-CRISIS-01 Schedule of Events

CCB-CRISIS-01 Schedule of Events	Screen	D1	D2 - D7 (± 8 hours)	Final Visit D15 (± 2 days)	F/U Phone Call 2 weeks/ Survival (± 3 days)
Procedures					
Informed Consent	X				
AE/Concomitant Medications	X	X	D7	X	
Medical history / History of current illness	X				
Demographics, collect Height and weight	X				
Check for Physical Exam abnormalities	X				
Pregnancy Test (urine or serum)	X				
Hematology/Chemistry	X	X (pre-dose)	D7	X	
Inflammatory Markers*		X (pre-dose)	D3, D5, D7	X	
DHO/brequinar PK Sample Collection & Processing		X (pre-dose)	D3, D5, D7	X (DHO only)	
Swab collection for nasopharyngeal viral load		X (pre-dose)	D3, D5, D7	X	
Clinical SARS-CoV-2 testing RT-PCR	X				
Hospital Status			D3, D5, D7	X	
NEWS2 Assessments		X	D3, D5, D7	X	
Dispense Study Medication if assigned to brequinar		X	D2 – 5		
Drug Accountability			D7		
Survival Assessment Day 29					X

Collect information from available electronic health record (EHR), Progress Notes, and medication records; a special visit by research staff is not to be performed. Hematology, Results for Chemistry and available inflammatory markers analyzed locally are to be obtained from the EHR; do not draw another set of labs. Missed samples due to hospital staff too busy or for technical reasons unable to obtain samples will not be counted as protocol deviations.

Note that any visits other than Screening/Day 1 may be conducted via telephone or digital media. Missed samples/assessments when phone visits occur will not be counted as protocol deviations.

\*Inflammatory markers are to be collected from the EHR when available; otherwise process and ship samples to the central laboratory per the Laboratory Manual. DHO and brequinar samples will also be sent to the central laboratory.

Note that if the subject is discharged before Day 15, ensure safety laboratory samples for hematology and chemistry are obtained prior to discharge and on an outpatient basis per Section 8.4.

PROTOCOL NUMBER: CCB-CRISIS-01  
PROTOCOL VERSION DATE: 01MAY2020

Page 53 of 55

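### SAEs and drug-related AEs are to be collected after Day 15, but apart from bleeding questions for subjects discharged before Day 7, no scheduled procedure after Day 15 asks about them (version 01MAY2020)

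*Protocol*

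**What the plan says.** All references are to the 01MAY2020 version, the latest one whose full text is shown.

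- **What must be collected.** The synopsis states: "After Day 15, collect/record only Serious Adverse Events (SAEs) or those judged by the Investigator or designated person to be related to study drug". Section 10 repeats this. It restricts SAE reporting to suspected causal events only later: "Any serious adverse events (SAEs) experienced after 30 days post the last dose of study drug should only be reported to the sponsor". Up to that point every SAE is reportable.
- **What is scheduled.** The last visit with an AE review is Day 15 (± 2 days). Day 29 (± 3 days) in Section 9.5 reads "Determine survival status from EHR if available or contact the subject by phone call/digital media as acceptable to the institution", and the synopsis has the same content. In Appendix A the AE/concomitant medication row is marked at Screen, D1, D7 and D15. The follow-up column carries only "Survival Assessment Day 29".
- **How Day 29 is described elsewhere.** Sections 5 and 8.3 say mortality is assessed by phone or other digital media and mention no EHR route. Inclusion criterion 3 has subjects discharged before Day 15 agree to a Day 29 contact.
- **Exception.** Section 10.6 gives subjects discharged before Day 7 staff contacts on Days 7, 15 and 29. It says phone visits will ask about hematologic toxicity, using a list of bleeding signs.
- **Unscheduled visits.** Section 9.5.1 allows them for related AEs or SAEs with onset no more than two weeks after the final dose.

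**The concern.** The protocol orders data that its own visit schedule does not gather. A subject discharged on Day 9, for example, has a Day 15 contact and then, under Section 9.5, possibly only a chart check for survival. A readmission to another hospital, or a late drug-related event managed by a family doctor, enters the database only if someone reports it. The site's record need not show events, or even a death, that happened elsewhere.

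The primary endpoint in Section 6.1 is the rate of post-randomization AEs together with safety laboratory results. About 16 subjects are planned on brequinar, so one unrecorded event moves that arm's rate by 1/16 = 6.25 percentage points. An analysis plan cannot recover events that were not asked about.

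The contradictory descriptions of Day 29 also mean that sites may carry it out differently. The ± 3 day window lets the secondary endpoint, mortality through Day 29, be closed before Day 29.

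**Working it through.** The plan gives no figure for this point, so there is nothing to reproduce. The check is a count of days.

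**Inputs**
- Last planned dose: Day 5 (five once-daily doses, Section 8.1.1). It may be earlier if the subject is discharged before Day 5 (Section 8.4).
- Last scheduled AE enquiry: Day 15, or Day 13 to Day 17 with the visit window (Section 9.5 and Appendix A).
- Three candidate ends of the period: 30 days after the last dose (Section 10), Day 29 (end of scheduled follow-up), and 14 days after the last dose (Section 9.5.1).

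**Formula**

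Share after the last enquiry = (end day − enquiry day) / (end day − last-dose day)

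**Last dose on Day 5, enquiry on Day 15**
- 30-day SAE window, ending on Day 35: (35 − 15)/(35 − 5) = 20/30 = 67%.
- To Day 29: (29 − 15)/(29 − 5) = 14/24 = 58%.
- Two-week window, ending on Day 19: (19 − 15)/(19 − 5) = 4/14 = 29%.

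**Enquiry moved within ± 2 days (Day 17 to Day 13)**
- 30-day window: 18/30 to 22/30 = 60% to 73%.
- To Day 29: 12/24 to 16/24 = 50% to 67%.
- Two-week window: 2/14 to 6/14 = 14% to 43%.

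**Earlier last dose, enquiry on Day 15.** For a last dose on Days 1 to 4, the 30-day share runs from 16/30 to 19/30, or 53% to 63%.

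So more than half of the 30-day SAE window follows the last scheduled enquiry when that enquiry is on Day 15. To Day 29 it is half or more with a Day 5 last dose. Against the two-week window it is a minority.

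Control subjects have no last dose. For them the comparable gap is Days 16 to 29, which is 14 days.

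**Effect of adding AE questions at Day 29** (last dose Day 5): enquiry would reach 29 − 5 = 24 of 30 days. The remainder falls from 20/30 (67%) to 6/30 (20%).

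**Mortality window.** 29 − 3 = Day 26, so an early check leaves Days 27, 28 and 29 unobserved, 3 of 29 days.

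**The case against.** The strongest reply is that Section 10 does not depend on scheduled questions. Sites must record what they learn. Related events are followed until they resolve or stabilise, and Section 8.3 extends monitoring beyond Day 15 when such events need it. Section 3.9 allows extra visits for AEs in the brequinar group. Early-discharge subjects receive a symptom list and are told to call. The 30-day sentence limits what is reported afterwards and does not promise 30 days of active questioning. All of this stands. The problem is therefore incomplete ascertainment and not total loss. It does not close the gap, because each of these routes starts only after an event has come to the site's notice.

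Three stronger readings are tempting, and the documents do not support them.
- A reader might infer that the late period is not asked about at all. Section 10.6 rules that out for subjects discharged before Day 7, although the stated questions concern hematologic toxicity and bleeding and not SAEs in general.
- A reader might set the Day 15 stop for all AEs against the reference in Section 8.2.1, "AEs through 21 days showed that 2 of 39 subjects (5.1%) had a severe", and ask for all AEs to Day 21. That reference counts drug-related events, which this trial still records after Day 15. The required collection period is not shorter like for like, and collecting all AEs to Day 21 would not match it.
- A reader might conclude that the suspension rule in Section 10.6, "If the rate or severity of hematologic toxicities appears to be above the expected rate", is tilted toward no signal. That section does not tie its expected rate to the 21-day data. The review works from available hematology data, to which a phone question adds no laboratory values.

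It is also fair that the mortality window is an ordinary visit window on a secondary, descriptive endpoint. The 05JUNE2020 table of contents adds sections on stopping criteria, Grade 3 or 4 toxicity follow-up, infection follow-up and a DSMB review schedule, so safety follow-up was revised. Those texts are not shown, and whether the gap remained cannot be checked.

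**Conclusion.** The point holds as an internal contradiction with a measurable gap. SAEs and drug-related AEs are required after Day 15, but outside the Section 10.6 exception no scheduled procedure asks for them. Section 9.5 and the synopsis also allow an EHR check where Sections 5 and 8.3 and criterion 3 describe a contact.

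The share after the last scheduled enquiry is 67% of the 30-day SAE window, 58% to Day 29, or 29% of the two-week window. All three assume a Day 5 last dose and a Day 15 visit, and all three should be given, since the choice of window decides whether the gap is the larger part.

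The consequence is possible under-ascertainment of late SAEs and related AEs in the primary safety endpoint, and up to three uncovered days for mortality. The documents give no basis for estimating how many events would be lost. In a descriptive study of about 24 subjects this is a worthwhile, inexpensive improvement and not a threat to the trial's validity.

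**What to change.** Reconcile the Day 29 text in the synopsis, Section 9.5 and Appendix A with Sections 5, 8.3, 10 and 10.6 and inclusion criterion 3:

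- Make Day 29 a direct contact for every surviving subject in both arms, with an EHR check in addition and not as a substitute.
- Ask about SAEs (including readmission) and possibly drug-related AEs since Day 15, with onset dates.
- Mark the AE row of Appendix A for this contact.
- Record the date of death, and use a window of 0 to +3 days so that mortality is not closed before Day 29.

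The cost is amendment wording and a few questions in a contact that already exists. The 31MAR2020 schedule marked the AE row at this same follow-up call, so the step is workable. The downsides are two-week recall and slightly more data entry. Days 30 to 35 of the 30-day window would still rest on spontaneous reporting when the call is made on Day 29. The sponsor should first check whether a version after 01MAY2020 already makes the change.
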